## 5. STATISTICAL ANALYSES

### 5.1. General Considerations

All data will be analyzed descriptively per vaccine group. Continuous variables will be summarized using the following statistics, as appropriate: number of observations, mean, standard deviation (SD), median, quartiles (Q1 and Q3), minimum, and maximum. The minimum and maximum will be reported to the same number of decimal places, the mean, median, lower, and upper quartile will be reported to one more decimal place and the SD will be reported to two more decimal places than the raw data recorded in the database. Frequencies and percentages (one decimal place) will be generated for categorical variables. Percentages will not be presented for zero counts.

#### 5.1.1. Study Phases

A baseline (or reference) value will be defined as the value of the last available assessment prior to the vaccination on Day 1.

The safety analysis will present all results by phase. Immunogenicity results will be presented per scheduled time point as appropriate. Listings will be shown per phase and time point.

Study day or relative day is defined as follows:

- Study Day = visit date – date of Day 1 + 1; if visit date  $\geq$  date of Day 1 (date of first vaccination).
- Study Day = visit date – date of Day 1; if visit date  $<$  date of Day 1 (date of first vaccination).

### 5.1.2. Phase Definitions

The phases in the study will be constructed as follows:

**Table 1: Phase Definitions**

Phase	Phase #	Period	Period #	Interval	
				From	To
Screening	1			Date and time of signing the informed consent form a	One minute prior to start of Post-dose 1 period
Regimen	2	Post-dose 1	1	Date and time of first vaccination	Minimum of: a) 23:59 at the date of last contact (for early discontinuation) b) 23:59 at the date of database cut-off date in case of interim c) 23:59 on 28 days after the first vaccination (23:59 of day of vaccination + 28 days) d) One minute prior to Post-dose 2
Follow-up 1	3	Follow-up 1		One minute after post-Dose 1 period end	Minimum of: a) 23:59 at the date of last contact (for early discontinuation) b) 23:59 at the date of database cut-off date in case of interim c) One minute prior to Post-Dose 2
Regimen	2	Post-dose 2	2	Date and time of second vaccination	Minimum of: a) 23:59 at the date of last contact (for early discontinuation) b) 23:59 at the date of database cut-off date in case of interim c) 23:59 on Day 28 after the second vaccination (23:59 of day of vaccination + 28 days)
Follow-up 2	4	Follow-up 2		One minute after Post-dose 2 period end	Minimum of: a) 23:59 at the date of last contact b) 23:59 at the date of database cut-off date in case of interim

a In case an earlier date is available (e.g., for lab or vital signs), then use the very first date to include all data.

Note: participants who did not receive a second vaccination will not have a Post-dose 2 or Follow-up 2 period.

The periods/phases will be used primarily for allocation of adverse events to various time periods during the study. Adverse events will be summarized for each of the active periods, 'Post-dose 1' and 'Post-dose 2', as well as Post-dose 1 and Post-dose 2 Combined, which is referred to as

‘Regimen’. Additionally, for SAEs and AEs leading to discontinuation of study vaccine tables, an ‘Entire study’ period will be defined. ‘Entire study’ covers the time window from vaccination 1 up to and including the end of the study for each participant.

### 5.1.3. Visit Windows

For the immunogenicity analysis, assessments will be allocated to an analysis visit based on the planned visit as captured in the CRF. Visits that are out of the immunogenicity analysis (broad) visit windows (see [Table 2](#)) will not be included in the per-protocol immunogenicity analysis. However, they may be included in sensitivity analyses.

**Table 2: Visit Windows for Immunogenicity Analysis**

CTP Visit Day	Reference day	Target day (from reference day)	CTP visit (narrow)		Immunogenicity analysis (broad)	
			Window	Relative day	Window	Relative day
Day 1	Vac 1	Day 1	[0; 0]	[1;1]	[0; 0]	[1;1]
Day 8	Vac 1	Day 8	[0;2]	[8;10]	[-2;3]	[6;11]
Day 29	Vac 1	Day 29	[-3;3]	[26;32]	[-7;10]	[22;39]
Day 57	Vac 1	Day 57	[-3;3]	[54;60]	[-10;10]	[47;67]
Day 64	Vac 2	Day 8	[0;2]	[8;10]	[-6;7]	[2;15]
Day 85	Vac 2	Day 29	[-3;3]	[26;32]	[-14;14]	[15;43]
Day 238	Vac 2	6 months	[-14;14]	[168;196]	[-21;21]	[161;203]
Day 365	Vac 1	12 months	[-30;30]	[335;395]	[-84; $\infty$ ]	[ $\geq$ 281]

Time windows may be redefined prior to unblinding if the number of samples excluded as per the definitions above are too numerous.

## 5.2. Participant Dispositions

Participant information will be shown for the full analysis set.

The number of participants in the following disposition categories will be summarized throughout the study by intervention group and overall:

- participants screened
- participants randomized
- participants vaccinated and not randomized
- participants randomized and not vaccinated
- participants in the Full Analysis Set (FAS)
- participants in the Per-protocol Immunogenicity (PPI)
- participants who discontinued study
- participants who discontinued vaccination
- reasons for termination

Also, the number of participants and percentage per phase will be tabulated. The number of missed vaccinations will be tabulated.

### **5.2.1. Extent of Exposure**

The number and percentage of participants who receive study vaccination, as well as the number of days between the 1st and 2nd vaccination, will be summarized by intervention group and overall. The number and percentage of participants by visit (Day 1, Day 8, Day 29, Day 57, etc.) will similarly be summarized.

## **5.3. Primary Endpoint(s) Analysis**

### **5.3.1. Definition of Endpoint(s)**

Section 3 of the CTP provides AE definitions associated with primary safety endpoints. The primary endpoints to assess safety are:

- Occurrence, severity, duration, and relationship to study vaccine of solicited local and systemic AEs for 7 days after each vaccination.
- Occurrence, severity, duration, and relationship to study vaccine of unsolicited AEs for 28 days after each vaccination.
- Occurrence and relationship to study vaccine of SAEs from first vaccination to the end of the study.

### **5.3.2. Estimand**

Not applicable.

### **5.3.3. Analysis Methods**

No formal statistical testing of safety data is planned. Safety data will be analyzed descriptively per intervention group and overall for the FAS. The number and percentage of participants with at least one particular AE (solicited/unsolicited) will be tabulated. Only treatment emergent (with onset or worsening after first vaccination) AEs will be presented in the tables.

Solicited AEs will be summarized by class (local or systemic) and preferred term. Unsolicited AEs will be summarized by Medical Dictionary for Regulatory Activities (MedDRA) System Organ Class and Preferred Term.

For solicited AEs, the following tables will be provided:

- summary,
- by worst severity grade,
- at least grade 3,
- related (systemic only),
- at least grade 3 related,

- time to onset (in days) from the start of each vaccination period and duration (in days), and
- body temperature.

Note: Duration is defined as number of days from the start of the event until resolution of the event. The time to first onset is defined as (date of first onset – reference date + 1). The reference dates are the start dates of all prior vaccination periods (i.e., the prior vaccination dates for dose 1 or dose 2).

For unsolicited AEs, the following tables will be provided:

- summary table (including SAEs, fatal outcome, and discontinuation),
- all events,
- at least grade 3,
- related,
- at least grade 3 related,
- SAEs
- time to onset (in days) from the start of each vaccination period and duration (in days).

## **5.4. Secondary Endpoint(s) Analysis**

### **5.4.1. Key Secondary Endpoint**

#### **5.4.1.1. Definition of Endpoint**

The secondary endpoint to evaluate immunogenicity is the magnitude of antibodies binding to the stem or the full-length HA protein as measured by enzyme-linked immunosorbent assay (ELISA).

#### **5.4.1.2. Estimand(s)**

Not applicable.

#### **5.4.1.3. Analysis Methods**

The analysis methods are described in Section [5.7.1](#).

## **5.5. Tertiary/Exploratory Endpoint(s) Analysis**

Exploratory endpoints relating to immunogenicity are described in Section [5.7.1](#) and corresponding subsections.

Exploratory endpoints relating to evaluation of the virology objective include:

- Signs and symptoms of influenza-like infection (ILI)

Confirmation of infection by reverse transcriptase polymerase chain reaction (RT-PCR). Refer to section CTP 8.1.1. ILI Procedures for data collection details.

Two dimensions (symptom intensity and impact) are collected using 5 scales (3 to 7 items in each scale) from the FLU-iiQ questionnaire:

1. Symptom intensity
  - respiratory symptoms (3 items)
  - systemic symptoms (7 items)
2. Impact
  - daily activities (6 items)
  - other people (5 items)
  - emotions (4 items)

The items within scales are coded (0=None, 1=Mild, 2=Moderate, 3=Severe), then scales are averaged [scale score divided by the number of items], thus each scale ranges from 0 to 3.

Total score (average of all 5 scales), total symptom intensity score (average of respiratory symptoms and systemic symptoms score) and total impact score (average of daily activities, other people, and emotions scores) will be calculated. If more than 50% of data from one scale is missing, then the value for that scale for that individual is coded as missing.

Descriptive statistics by intervention group might be provided for each scale of FLU-iiQ evaluating signs and symptoms for subjects developing ILI during the influenza season, if more than 10 participants report symptoms. Otherwise, listing of FLU-iiQ responses will be provided.

The number and percentage of participants who have signs and symptoms of ILI and confirmation of influenza infection by RT-PCR or response to ILI by serology will be summarized.

## **5.6. Other Safety Analyses**

Safety analyses will be performed on the FAS. Continuous variables will be summarized using the following statistics, as appropriate: number of observations, arithmetic mean (mean), 95% CI for the mean (if applicable, large studies), standard deviation (SD), standard error (SE), median, quartiles (Q1 and Q3), minimum, and maximum. Frequencies and percentages (one decimal place) will be generated for categorical variables. No formal comparisons between groups will be provided.

Two types of safety tables will be shown. In the by regimen layout, safety data will be analyzed by study intervention regimens as designed per protocol. In case of multiple vaccinations, data will be presented by phase as well as over the entire regimen. The denominator for the percentages is the number of participants in the considered population and phase for a certain regimen (incidence per 100 participants/phase). In the second, by vaccine layout, only limited safety data will be presented by the different vaccines used in the study but by considering every vaccination administered as a separate safety episode. The denominator for the percentages is the number of vaccinations administered of a certain vaccine (rate per 100 vaccinations of a particular vaccine). DPS will define which tables will be provided by vaccine layout.

## **5.6.1. Adverse Events**

### **5.6.1.1. Definitions**

Solicited AEs are used to assess the reactogenicity of the study vaccine and are predefined local events (pain/tenderness, erythema, and swelling at the injection site) and systemic events (fatigue, headache, nausea, myalgia, and fever) for which the participant is specifically questioned, and which are noted by participants in their reactogenicity diary. Unsolicited AEs are all AEs for which the participant is not specifically questioned.

Solicited AEs shown in the tables are extracted from the investigator assessment pages (CE) of the CRF. For unsolicited AEs, only the AEs within the 28-day period following each vaccination will be presented in the safety tables. SAEs will be captured and tabulated in the outputs covering the whole study period. All other collected unsolicited adverse events will be presented through listings.

The verbatim terms used in the eCRF by investigators to identify AEs will be coded using the Medical Dictionary for Regulatory Activities (MedDRA).

Solicited administration site symptoms will be considered as related to the study vaccine.

The severity of the AEs will be classified as grade 1 to 4. Solicited events that are graded less than grade 1, are not considered as AE. In case no grades are available, the grading of the solicited events will occur according to the grading list in Appendix 6.

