All SAEs and AEs leading to discontinuation from further study vaccination (regardless of the causal relationship) are to be reported from the moment of first vaccination until completion of the participant's last study-related procedure, which may include contact for safety follow-up. The sponsor will evaluate any safety information that is spontaneously reported by an investigator beyond the time frame specified in the protocol.

AEs of Grade 3 or Above that are Related to Study Vaccine

All AEs of Grade 3 or above that are related to study vaccine must be reported to the appropriate sponsor contact person by study-site personnel immediately, but no later than 24 hours of their knowledge of the events. Relevant AE information should be updated in the eCRF on the same day when the AE information is collected (see Section 6.8 Study Pausing Rules).

Serious Adverse Events

All SAEs occurring during the study must be reported to the appropriate sponsor contact person by study-site personnel immediately, but no later than 24 hours of their knowledge of the event.

Information regarding SAEs will be transmitted to the sponsor using the Serious Adverse Event Form, which must be completed and signed by a physician from the study site, and transmitted to the sponsor immediately, but no later than 24 hours of their knowledge of the event. The initial and follow-up reports of an SAE should be transmitted in a secure manner electronically or by facsimile (fax). Telephone reporting should be the exception and the reporter should be asked to complete the appropriate form(s) first.

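### SAP 5.6.1.1 and SAP 5.1.2 give different tabulation periods for AEs that stop study vaccine, so a non-serious AE starting after Day 29 that stops dose 2 may reach only a listing

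*SAP*

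**What the plan says.** Four places bear on how an AE that stops study vaccine is reported.

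- **SAP 5.6.1.1 (Definitions).** For unsolicited AEs, "only the AEs within the 28-day period following each vaccination will be presented in the safety tables". One exception follows: "SAEs will be captured and tabulated in the outputs covering the whole study period". The remainder is then disposed of: "All other collected unsolicited adverse events will be presented through listings".
- **SAP 5.1.2 (Phase Definitions, text after Table 1).** Besides the post-dose periods, an *Entire study* period is to be defined "for SAEs and AEs leading to discontinuation of study vaccine tables". That period "covers the time window from vaccination 1 up to and including the end of the study for each participant".
- **SAP 5.3.3 (Analysis Methods).** This section, to which SAP 5.6.1.2 sends the reader for the AE analysis, lists the unsolicited AE tables. SAEs have their own table. Discontinuation is named only as a component of the summary table, with no period.
- **Protocol 8.3.1.** On collection, which runs from dose 1 to the participant's last study procedure: "All SAEs and AEs leading to discontinuation from further study vaccination (regardless of the causal relationship) are to be reported from the moment of first" […].

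Protocol 9.4.2 and SAP 2 both single out AEs leading to vaccine discontinuation, with SAEs and Grade 3/4 AEs, for particular attention in the safety analysis.

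**The concern.** The two SAP rules cannot both be applied to a non-serious AE that starts more than 28 days after dose 1 and causes dose 2 to be withheld. Under 5.1.2 it belongs in a table covering the whole study. Under 5.6.1.1 it is neither within 28 days of a vaccination nor serious, so it goes to a listing. Section 5.6.1.1 does not refer to 5.1.2, and 5.3.3 does not say which period its discontinuation entry uses, so a programmer could follow either text.

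At stake is the completeness of one tabulated count, by group, in a safety category that both documents say they will watch. The study gives two injections, on Day 1 and Day 57. An AE that stops vaccination therefore has only the second injection to stop, and part of the interval before that injection lies outside the 28-day window.

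**Working it through.** The plan states no figure to reproduce. The check sets the rules side by side and does the day arithmetic.

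**Step 1. Where the 28-day window ends.** SAP 5.1.1 defines study day, on or after first vaccination, as date minus date of Day 1, plus 1. Unless cut short by early discontinuation, a data cut-off or dose 2, SAP Table 1 (Phase Definitions) closes Post-dose 1 at "23:59 on 28 days after the first vaccination (23:59 of day of vaccination + 28 days"). The vaccination day is Day 1, so the window closes at the end of Day 1 + 28 = **Day 29**.

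**Step 2. What comes next.** Follow-up 1 starts "One minute after post-Dose 1 period end", that is, on **Day 30**. With dose 2 planned for Day 57, the nominal gap is Days 30 to 56: 56 − 30 + 1 = **27 days**. Across the ±3-day visit window:

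- Dose 2 due on Day 54: Days 30 to 53, 53 − 30 + 1 = 24 days.
- Dose 2 due on Day 60: Days 30 to 59, 59 − 30 + 1 = 30 days.

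A participant who never receives dose 2 has no Post-dose 2 or Follow-up 2 period (note to SAP Table 1). For that participant Follow-up 1 runs on to last contact or data cut-off.

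**Step 3. Which events are affected.** SAP 5.6.1.3 allocates unsolicited AEs by start date.

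| AE that stops dose 2 | Under 5.6.1.1 | Under 5.1.2 |
|---|---|---|
| Starts by Day 29, serious or not | Tabulated | Tabulated |
| Starts after Day 29, serious | Tabulated (SAE exception) | Tabulated |
| Starts after Day 29, non-serious | **Listing only** | **Tabulated** |

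The rules disagree only in the last row. An AE that began by Day 29 and was still present when dose 2 was withheld is unaffected, because its start date places it in Post-dose 1.

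**Step 4. Size per case.** Each active arm has 25 participants (Protocol 4.1, Table 1). One omitted case changes that arm's tabulated percentage by 1/25 = **4 percentage points**. The documents give no expected number of such cases, so no total can be calculated.

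**The case against.** The best defence is that 5.1.2 is the specific rule and 5.6.1.1 a general sentence in a definitions section. Section 5.1.2 names tables of AEs leading to discontinuation, so it presupposes that they exist, and it gives them a period that includes Days 30 to 56. On that reading only a cross-reference is missing. This is probably the intent. It does not remove the conflict, because 5.6.1.1 also names a specific exception, names SAEs alone, and assigns everything else to listings.

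A second defence is that the Data Presentation Specifications may settle the matter, since SAP 1 and SAP 5.8 leave mock-ups, programming instructions and the choice of outputs to them. They are not among the documents reviewed, so this cannot be excluded. They should still carry out a consistent SAP and not have to choose between two of its rules.

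A third is that the 28-day limit follows the primary endpoint for unsolicited AEs. That is correct, and the limit should stay for other non-serious unsolicited AEs.

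A reader might also infer more than the documents support:

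- **That about half of such events would be lost.** The gap is 27 of the 56 days before dose 2 (48%), but that is a share of calendar days. Reading it as a share of events needs onset to be uniform over the interval, for which the documents give no basis.
- **That a mismatch with the disposition table would reveal the error.** SAP 5.2 counts everyone who discontinued vaccination. Protocol 7.1 includes non-AE reasons such as pregnancy or withdrawn consent to further vaccination, so the two counts need not agree anyway.
- **That the events are hidden, or are a main signal for regimen choice.** They are collected and listed, the stop is counted in disposition, and Protocol 9.4.2 allows narratives for participants who stop because of an AE. Nothing in the documents gives late-onset, non-serious AEs a leading role in selecting the regimen.

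**Conclusion.** The inconsistency is real and narrow. Read literally, SAP 5.6.1.1 leaves a non-serious AE with onset after Day 29 that stops dose 2 out of the tabulated count, while SAP 5.1.2 would include it. Each such case is worth 4 percentage points in an arm of 25. Such cases are likely to be few.

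This rests on two assumptions: that 5.6.1.1 is applied as written, and that the unseen Data Presentation Specifications do not override it. The documents do not show a decision to omit these events, and nothing here affects data collection, the primary endpoint definitions or the sample size. It should be corrected because the category is one the plan itself singles out and the correction is easy.

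**What to change.** 1. In SAP 5.6.1.1, widen the exception. For example: *Serious AEs, and AEs leading to discontinuation of study vaccine, are tabulated over the Entire study period defined in Section 5.1.2; other unsolicited AEs outside the 28-day windows are listed.*
2. In SAP 5.3.3, state that the discontinuation row of the unsolicited AE summary, or a separate table if one is produced, uses the *Entire study* period.
3. Check that the Data Presentation Specifications follow the same rule.

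The cost is a small change of SAP wording and, at most, one small table. The data are already collected under Protocol 8.3.1.

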### **5.6.1.2. Analysis of Adverse Events**

Analysis of adverse events is described in Section [5.3.3](#).

Unsolicited AEs may also be presented for Standardized MedDRA Queries (SMQs) to facilitate review of certain classes of unsolicited AEs.

### **5.6.1.3. Phase Allocation of Adverse Events**

#### **Step 1: Allocation of events to the periods:**

Solicited events are always allocated to the respective Post-dose period.

Unsolicited adverse events are allocated to periods based on their start date/time. If the start date/time of an event falls between (or on) the start and stop date/time of a period, the AE is attributed to that period (treatment-emergent principle).

- In case of partial start or stop dates (i.e. time and/or day and/or month and/or year missing), the events are allocated to the periods using the available partial information on start and end date; no imputation will be done. If, for instance, the AE start date only month and year are available, these data are compared to the month and year information of the periods. This rule may lead to multiplication of the event as a consequence of its assignment to multiple periods.

- In case of a completely missing end date, the date is imputed by the cut-off date of the analysis for participants still ongoing in the study, and by the end date of the last period for participants who discontinued or completed the study. In case of a completely missing start date, the event is

allocated to the first active treatment phase (Post-dose 1 period), except if the end date of the AE falls before the start of the first active treatment phase (Post-dose 1 period).

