1. Events can only be combined into one and the same AE if their start and stop dates are known.
2. In case the completely missing end date is imputed (for period allocation), this date is also considered as a complete date.
3. Time is not considered when determining overlap of events.

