**5.6.1.4. Missing Data**

Missing data will not be imputed. Participants who do not report an event will be considered as participants without an event. An AE with a missing severity or relationship will be considered as an AE reported, but will be considered as not reported for the severity or relationship. For example,

an AE with missing severity will be considered as an AE reported for the analysis of any grade but will be considered as not reported for the analysis of at least grade 3.

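### AE duration is part of the primary endpoints, but the SAP has no valid duration for an AE without a resolution date, and its end-date imputation reaches the duration of combined events

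*SAP*

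**What the plan says.** SAP 5.3.1 names duration in two primary endpoints: "Occurrence, severity, duration, and relationship to study vaccine of solicited local and systemic AEs for 7 days after each vaccination" and "Occurrence, severity, duration, and relationship to study vaccine of unsolicited AEs for 28 days after each vaccination". The third primary endpoint, on serious AEs, does not include it. SAP 5.3.3 plans a table of time to onset and duration for both kinds of AE and gives this definition: "Duration is defined as number of days from the start of the event until resolution of the event". According to the version history, SAP 2.0 widened the solicited table from the most frequent events to all of them.

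SAP 5.6.1.3, Step 1, deals with missing end dates: "In case of a completely missing end date, the date is imputed by the cut-off date of the analysis". This applies to anyone who has not yet left or finished the study. For participants who discontinued or completed, the end date of their last period is used instead.

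Step 2 of the same section merges records of one participant that share a preferred term and overlap or follow each other within a day. Merged records are given a common onset, period and total duration. The remarks allow merging only when start and stop dates are known, and then add: "In case the completely missing end date is imputed (for period allocation), this date is also considered as a complete date".

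SAP 5.6.1.4 begins "Missing data will not be imputed". The rest of that section covers events not reported, missing severity and missing relationship. It does not mention end dates or duration.

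**The concern.** An AE that is still ongoing, or whose end was never recorded, has no resolution date, so the definition in 5.3.3 cannot be applied to it. Such events are foreseeable. Protocol 4.1 (Study Procedures) follows AEs until they resolve or stabilise, and a stabilised AE has no resolution date. Protocol 2.3.1 also cites persistent injection-site nodules with aluminum adjuvants.

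If an imputed date stands in for resolution, a censored time is stored as if it had been observed, and its length depends on when the data are cut. If unresolved events are left out, the longest ones leave the summary. In a first-in-human study, the duration tables are where a reader looks for persistent reactions, so the table should show plainly which durations are complete.

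**Working it through.** The documents give no figure for AE duration, so there is nothing to reproduce. The check is to trace whether an imputed date can enter a duration, and then to size the effect on assumed data. Durations below are counted inclusively (end day minus onset day + 1). SAP 5.3.3 does not say whether to add 1; without it each value is one day shorter.

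**1. Route through combined events.** Take one participant and one preferred term. Record A runs from Day 3 to Day 6. Record B starts on Day 6 and has no end date.
- Step 1 sets the end of B to the analysis cut-off, or to the end of the last period.
- The remarks to Step 2 treat that date as complete, so A and B qualify for merging.
- Both start within the same post-dose period, so Step 2 makes them one AE with one total duration, counted from Day 3.

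Resulting total duration:
- participant on Day 85 at cut-off: 85 − 3 + 1 = 83 days
- participant on Day 238 at cut-off: 238 − 3 + 1 = 236 days
- completed, last contact on Day 365: 365 − 3 + 1 = 363 days

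Nothing about the event has changed between these values. If it is truly ongoing, each is a lower bound. If it ended and the date was not recorded, each is usually too long. No flag tells the two apart.

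**2. Single unresolved AE.** Step 2 does not apply, because there is nothing to merge. The Step 1 date is described as being for period allocation, and 5.6.1.4 is silent on end dates. No rule for the duration remains.

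**3. Size, on assumed data.** Five resolved AEs last 2, 3, 3, 3 and 4 days. A sixth starts on Day 5 and does not resolve. The figures are illustrative only.
- Sixth left out: mean 15/5 = 3.0, median 3.0
- Sixth ended at Day 85 (81 days): mean (15 + 81)/6 = 16.0, median 3.0
- Sixth ended at Day 365 (361 days): mean (15 + 361)/6 = 62.7, median 3.0

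The median is 3.0 days in all three cases. The maximum goes from 4 to 81 to 361.

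**4. More unresolved events, on assumed data.** Ten AEs last 1, 1, 2, 2, 2, 3, 3, 3, 4 and 5 days when all are resolved (mean 2.6, median 2.5). The longest are then made unresolved, with onset on Day 3.
- 1 of 10 unresolved: imputing gives a mean of 10.4 (Day 85) or 38.4 (Day 365) and a median of 2.5; leaving it out gives a mean of 2.3 and a median of 2.0
- 5 of 10 unresolved: imputing gives a median of 42.5 (Day 85) or 182.5 (Day 365); leaving them out gives 2.0

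One unresolved event is enough to move the mean. The median moves little until about half are unresolved. With none unresolved, the two approaches agree.

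**The case against.** The strongest reply is that neither cited rule is a duration rule. The imputation sits under phase allocation and is labelled for that purpose, and 5.6.1.4 deals with other kinds of missing data. This stands for a single AE: the SAP does not say that its imputed end date feeds duration, nor that unresolved events are dropped. A reader might infer that the duration tables are wrong under either rule. The documents do not support that, because the two sections are not rival instructions on duration. The reply does not remove the combined-event route, which is written out in Step 2 and its remarks.

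The route is also narrow. It needs at least two records with the same term, overlapping or adjacent, and a completely missing end date. Whether it covers solicited AEs is unclear, because the date rules follow the sentence on unsolicited events. AE follow-up limits missing end dates. SAP 5.1 lists median, quartiles and extremes as well as the mean, so an outlier would be visible. SAP Section 1 places mock-ups and programming instructions in the separate Data Presentation Specifications, which may already carry a column for ongoing events. All of this limits the size. A derivation for a primary-endpoint component still belongs in the SAP.

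Two further inferences should be resisted:
- **That cut-off imputation makes low-dose events look longer than high-dose ones.** Only the first 17 of the 60 Cohort 1 participants must precede Cohort 2; the other 43 may enrol alongside it (Protocol 4.1). At the final analysis, completers take the end of their last period rather than a calendar cut-off.
- **That persistent AEs would be hidden from the study.** Occurrence, severity and relationship tables count an AE whether or not it has resolved, and the pausing rules in Protocol 6.8 use persistence directly.

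**Conclusion.** The point holds as a gap in derivation with one written leak. An AE without a resolution date has no valid duration under the SAP. Where records are combined, the text assigns a duration that runs to the cut-off or the end of the last period and changes from one analysis to the next. For single unresolved AEs the rule is missing, and a summary of resolved events only would tend to be too short.

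The number of AEs without a resolution date cannot be known from the documents, so the effect on this trial's tables cannot be stated. On the assumed data, one unresolved event in six moves the mean from 3.0 to 16.0 or 62.7 days and leaves the median at 3.0. The safety analysis is descriptive, so no test, error rate or power is affected. The change is worth making because it is cheap and concerns a primary-endpoint component.

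**What to change.** - In SAP 5.3.3 and 5.6.1.3, state that an imputed end date is used only to allocate an event to a period and to decide whether records combine, and never to compute duration.
- In 5.6.1.3, Step 2, flag the total duration of a combined event with an imputed end as censored at the last assessment.
- In the duration tables, report for each group the number of AEs ongoing or with unknown end date beside a median duration, and list unresolved events as greater than x days, ongoing. The six-event example would then read: median 3.0 days, 1 of 6 ongoing.
- In 5.6.1.4, add a cross-reference to this rule, and say whether the end-date rule covers solicited AEs.

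A Kaplan-Meier summary is optional; in groups of 25, where only participants with the event contribute, the median with the count of ongoing events is enough. The cost is a few sentences in the SAP and one table column, with no change to data collection.
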